# 17.3.3.2 Primary endpoint analysis

Additional exploratory analyses will be undertaken of the potential impact of tumour biomarkers on treatment efficacy and prognosis. The analyses of these outcomes will be decided upon depending on data structure and nature, i.e. whether to use one measurement or multiple measurements per individual. Appropriate multilevel approaches will be implemented in case of the later. Suitable variable transformations will be applied if required by modelling assumptions. Missing data patterns will also be evaluated and appropriate methodologies and sensitivity analyses will be used to assess the results sensitivity compared to the statistical assumptions.

## 17.3.3.3 Secondary endpoint analysis

Overall survival

Overall survival and cancer specific survival analyses at 2 and 5 years will be treated in the same manner as progression free survival analysis.

Pathological Response/assessment of tumour regression

Pathological tumour response will be assessed for all patients and comparisons examined using the chi-squared test with 95% confidence intervals expressed for response rates.

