#### **5.1 Secondary end points**

- Recurrence free survival at 5 years
- Overall survival at 2 and 5 years
- Colon cancer specific death at 2 and 5 years
- Artesunate drug related toxicity
- Adverse events
- Pathological assessment of tumour regression (involvement of lymph nodes; serosa; resection margin)
- Patient Quality of Life (assessed using validated EuroQol EQ-5D, EORTC QLQ C-30, EORTC QLQ C-29 quality of life tools)
- Surgical morbidity/mortality
- Predictive value of tumour biomarkers in terms of predicting response to artesunate therapy
- Biomarker and molecular profiling studies

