# 17.3.3 Statistical analysis plan

The event of interest (failure defined as cancer recurrence from a survival analysis perspective) is defined as the first recurrence of the disease after the patients' treatment allocation and surgery. Patients will be followed-up for 2 years; if the event of interest does not occur the patient will be considered (right) censored. The general assumption for time-to-event (survival analysis) is that the censoring is non-informative, i.e. it is independent of the event process. The Cox proportional hazard (PH) model would be applied to investigate the hazard ratio of disease recurrence for the artesunate group versus placebo group. The semi-parametric technique allows no assumption to be made on the baseline hazard; nevertheless proportionality of the hazards in the two arms should hold. The latter assumption can be tested on the basis of Shoenfeld residuals after fitting the model to the data.

We discussed an interim analysis in December 2021 with the DMC and TSC. At this time point 78 patients will have reached the primary end point (recurrence free survival 2 years after surgery). This analysis will be performed by an independent trial statistician familiar with both trials ([name]) and a report presented to the DMC and TSC members for review and recommendations thereafter.

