#### 17.3.3.1 Summary of baseline data and flow of patients

Details of the number of patients eligible for the trial, the number of patients consenting and the number randomised along with a breakdown for each group of the numbers of participants assigned, receiving the intended treatment, completing the study protocol, and analysed for the primary outcome will be clearly documented. This information will be displayed as a flow diagram (http://www.consort-statement.org/).

The analyses will be performed in STATA (StataCorp. 2014. Stata Statistical Software: Release 14. College Station, TX: StataCorp LP.) and/or (R: A language and environment for statistical computing. R Foundation for Statistical Computing, Vienna, Austria. ISBN 3-900051-07-0, URL http://www.R-project.org/). GraphPad (Prism) or other comparable statistical package.

Descriptive statistics, preliminary analysis and graphics will be used to understand the data structure, the nature of the variables and the appropriateness of the subsequent tests and analyses. Data will be summarized as mean, standard deviation and range if normally distributed. If the data are skewed then additional statistics such as median and inter-quartile ranges will be used to correctly describe the selected sample in the population. Parametric or non-parametric tests will be used as appropriate to ensure/verify that the two groups do not differ statistically with respect to any aspects but the intervention.

Three safety interim analyses are planned as the trial data collection proceeds, approximately after 10%, 50% and 75% of patients have completed their day 28 assessments.

The appropriate statistical framework for the analysis of the primary outcome is that of a survival analysis. Patients will be followed-up up to 2 years; if the event of interest does not occur within this time frame, the patient is considered (right) censored. The general assumption is that the censoring is independent of the event process. The Cox proportional hazard (PH) model would be applied to investigate the hazard ratio of disease reccurrence for the artesunate group vs. placebo group. The semi-parametric technique allows no assumption to be made on the baseline hazard; nevertheless proportionality of the hazards in the two arms should hold. The latter assumption can be tested on the basis of Shoenfeld residuals after fitting the model to the data.

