The inference is expressed in survival type metrics: i.e. proportion of individuals surviving recurrence beyond 1 year, 2 years and median time to recurrence in each group. Predictions (survival prognostics) will refer to the colon cancer population within our data range.

Missing data (attrition) will be assessed and sensitivity analysis will be employed upon the particularities exhibited by the data, i.e. missing data pattern and whether the missing information is associated with the main outcome. This will include data analysis under a 'missing at random assumption' and imputation methods tailored to interval censored data will also be applied.

Both a frequentist and Bayesian framework for statistical inference are envisaged. The uncertainty will be expressed in terms of 95% confidence intervals (CI) or 95% credible intervals (CrI) for their corresponding estimates. The frequentist statistical significance would be deemed at the 0.05 (5%) level.

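### Cancer-specific death borrows the recurrence analysis method; as written, other-cause deaths would be censored and the 2- and 5-year probabilities would come out slightly too high

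*Protocol*

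**What the plan says.** Section 5.1 lists "Colon cancer specific death at 2 and 5 years" among the secondary endpoints, and Section 17.2.2 repeats it. The one analysis rule for this endpoint is in Section 17.3.3.3: "Overall survival and cancer specific survival analyses at 2 and 5 years will be treated in the same manner as progression free survival analysis".

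The protocol describes a single time-to-event method, the recurrence analysis in Sections 17.3.3 and 17.3.3.1, so the cross-reference can only point there. Its components are:

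- **Event.** It "is defined as the first recurrence of the disease after the patients' treatment allocation and surgery". Death is not part of it.
- **Censoring.** Follow-up runs to 2 years, and "if the event of interest does not occur within this time frame, the patient is considered (right) censored".
- **Censoring assumption.** "The general assumption is that the censoring is independent of the event process" (Section 17.3.3 says the same in similar words).
- **Model.** "The Cox proportional hazard (PH) model would be applied to investigate the hazard ratio" for artesunate against placebo.
- **Reporting.** Survival-type quantities in each group, including the "proportion of individuals surviving recurrence beyond 1 year, 2 years".

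No section treats death from another cause as a competing event for cancer death. Section 17.5 allows that multistate modelling may be possible, but it does so in the context of the interim analysis and does not tie this to any endpoint.

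**The concern.** For recurrence or cancer death, a patient lost to follow-up can still have the event later, and censoring is the right device. A patient who has died of another cause can no longer die of colon cancer. If that death is censored, the survival curve behaves as though the patient's remaining risk were carried by those still alive. One minus that curve then estimates cancer death in a hypothetical population where nobody dies of anything else. It exceeds the real proportion dying of cancer whenever other-cause deaths occur.

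The listed endpoint is cancer death at two fixed times, so the affected quantity is the one to be reported. Other-cause deaths are plausible here: entry has a lower age limit of 18 but no upper limit (Section 9.1), patients undergo radical surgery, and follow-up lasts 5 years. At stake is the accuracy of an absolute risk in each arm, not the validity of the hazard ratio.

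**Working it through.** The protocol states no figure for cancer-specific or other-cause death, so there is none to reproduce for this endpoint. The check compares the two estimators.

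**Inputs**
- Times: 2 and 5 years (Sections 5.1 and 17.3.3.3).
- 5-year overall survival (OS): 60%. This is the background ceiling in Section 6.1 for colorectal cancer under current treatment, not a stage II/III figure. An assumed 75% is run as an alternative.
- Share of deaths from other causes, *s*: not in the protocol; assumed 5% to 50%.
- Constant cause-specific hazards and no other censoring: assumed.

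**Formulas.** Total hazard H = −ln(OS)/5, cancer hazard hc = (1 − s)H, other-cause hazard ho = sH.
- One minus survival, other deaths censored: 1 − exp(−hc·t).
- Cumulative incidence: hc/(hc + ho) × [1 − exp(−(hc + ho)t)].

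**Worked case, OS 60%, s = 20%.** H = 0.5108/5 = 0.1022, hc = 0.0817, ho = 0.0204.
- 5 years: 1 − exp(−0.4087) = 33.55%, against 0.8 × 0.40 = 32.00%. Excess 1.55 points.
- 2 years: 1 − exp(−0.1635) = 15.08%, against 0.8 × (1 − 0.6^0.4) = 14.78%. Excess 0.30 points.
- A simulation of 400,000 patients gave 33.6% against 32.0% and 15.1% against 14.8%.

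**Range with OS 60%**

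| Other-cause share | 2 years: censored / cumulative incidence (%) | Excess (points) | 5 years: censored / cumulative incidence (%) | Excess (points) |
|---|---|---|---|---|
| 5% | 17.64 / 17.56 | 0.09 | 38.45 / 38.00 | 0.45 |
| 10% | 16.80 / 16.63 | 0.17 | 36.86 / 36.00 | 0.86 |
| 20% | 15.08 / 14.78 | 0.30 | 33.55 / 32.00 | 1.55 |
| 30% | 13.33 / 12.94 | 0.39 | 30.06 / 28.00 | 2.06 |
| 50% | 9.71 / 9.24 | 0.47 | 22.54 / 20.00 | 2.54 |

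In relative terms the 5-year excess runs from about 1% to 13%. With OS 75% and the same shares, the excess is 0.03–0.16 points at 2 years and 0.16–0.90 points at 5 years.

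**Effect on the difference between arms.** Assume control hazards that would give 5-year probabilities of 20% for cancer death and 10% for other death, each taken alone. Then hc = 0.0446 and ho = 0.0211. Apply the design hazard ratio of 0.56 (Section 17.3.1, there for recurrence) to cancer death only.
- Control: 20.0% against 0.679 × 0.28 = 19.0%. Excess 1.0 point.
- Artesunate: hc = 0.0250, so 11.7% against 0.543 × 0.206 = 11.2%. Excess 0.6 points.
- The difference is distorted by about 0.4 points. With 100 patients per arm (200 randomised 1:1), its binomial standard error is about √(0.20 × 0.80/100 + 0.117 × 0.883/100) = 5.1 points.

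**The case against.** **The censoring is inferred.** The protocol never says that other-cause deaths are censored for this endpoint, and it never names Kaplan-Meier. The proportions it mentions are for recurrence at 1 and 2 years, and what it fixes most firmly is a Cox hazard ratio. This is fair, and it is why the point is conditional on following the cross-reference as written. It does not remove the point: the general rule censors anyone without the event of interest, and no exception is made for death.

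**It belongs in the statistical analysis plan.** Estimator detail often does, and that plan may already use cumulative incidence. But the protocol is not silent: it prescribes a method for this endpoint, and the remark on multistate models in Section 17.5 is optional and attached to something else.

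**It is a choice of estimand.** Under independent censoring, the censored curve has a conventional meaning as net cancer-specific survival. That stands if the result is labelled so. The listed endpoint, however, is colon cancer death at 2 and 5 years, which is naturally read as the probability of dying of the cancer.

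**The size is small.** This stands. The excess partly cancels between arms and lies well within sampling error.

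Two stronger readings are tempting but unsupported. A reader might infer that the borrowed 2-year censoring makes a 5-year result impossible. Section 17.3.3.3 itself names 2 and 5 years, and Sections 7.1 and 17.3.1 provide 5-year follow-up, so the method carries over with a longer horizon and only the wording is loose. A reader might also infer that the comparison of arms is invalid. With other-cause deaths censored, the Cox model still gives a valid cause-specific hazard ratio.

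**Conclusion.** The point holds in a limited form. Followed as written, Section 17.3.3.3 would censor other-cause deaths, and survival-type proportions read as the probability of colon cancer death would be too high in both arms. With 60% 5-year survival and an assumed 5–50% of deaths from other causes, the excess is about 0.1–0.5 points at 2 years and 0.5–2.5 points at 5 years; with 75% survival it stays below 1 point. These sizes rest on constant hazards and on an other-cause share that the protocol does not give; the upward direction does not depend on the share chosen. Overall survival, named in the same sentence, has no competing event and is unaffected, as is the cause-specific Cox hazard ratio. This is a minor improvement to one secondary endpoint and would be unlikely to change a conclusion.

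**What to change.** In Section 17.3.3.3, separate cancer-specific death from overall survival. For cancer death, keep the cause-specific Cox hazard ratio, and estimate the 2- and 5-year probabilities in each arm by cumulative incidence (Aalen-Johansen) with death from other causes as a competing event. Showing other-cause death by arm beside it would help the reader.

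As a clarification of wording only, state that the 2-year censoring in Sections 17.3.3 and 17.3.3.1 belongs to the primary analysis, and that 5-year analyses use all follow-up to 5 years.

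The cost is a sentence or two and standard code, with a small extra analysis and a slightly different reported figure. No new data are needed: Section 14.2 already requires all deaths to be reported whatever the cause, and the endpoint already requires cause of death to be classified.

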#### 9.1 Inclusion criteria

- 1. Aged 18 or over
- 2. Histologically proven single primary site colorectal adenocarcinoma or high grade dysplasia plus unequivocal radiological evidence of invasive cancer
- 3. Stage II/III colorectal cancer planned for surgical resection and no clinical indication for neoadjuvant preoperative chemotherapy/chemoradiation therapy
- 4. WHO performance status 0,1 or 2
- 5. Adequate full blood count: White Cell Count (WCC)  $>3.0 \times 10^9$  /l; Platelets  $>100 \times 10^9$ /l; Haemoglobin (Hb) >80g/L
- 6. Adequate renal function: Glomerular Filtration Rate >30ml/min by Cockcroft-Gault formula.
- 7. Adequate hepatobiliary function: Total bilirubin < 3 x Upper limit norm
- 8. Female participants of child bearing potential must have a negative pregnancy test <72 hours prior to initiating study intervention and agree to avoid pregnancy using adequate, medically approved contraceptive precautions for up to 6 weeks after the last dose of study treatment interventions.
- 9. Male participants with a partner of childbearing potential must agree to use adequate, medically approved contraceptive precautions during and for up to 6 weeks after the last dose of the study treatment intervention.
- 10. Patient able and willing to provide writen, informed consent for the study.

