#### 11.2 Randomisation procedure

Participants recruited to the study will be randomised to receive either artesunate or placebo 1:1. Randomisation will be by a computer-generated code. An unblinded randomisation list will be provided to each participating site and held in Pharmacy or held by a study coordinator that is not directly involved in the study. Following completion of the study the participant treatment allocation list held in the site Pharmacy files will be anonymised prior to collection by the Clinical Trials Monitor. The anonymised lists will be handed over to the statistician to facilitate data analysis.

All patients will be given a study specific 24 hrs emergency contact card immediately after being randomised. The card includes details of the Trial: Study title, details of IMP, patient trial number, CI/PI's contact details along with out of hours contact details in case of emergency.

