#### 12.5 Methods

**12.5.1 Samples** 

12.5.1.1 Obtaining, labelling, storing

Following informed consent, blood samples will be collected into vacutainer systems or similar tubes (usually 2 x 10 ml EDTA vacutainers) on D1 and D14/D15 of the study. The collected blood should be centrifuged, processed and stored at -80 $^{\circ}$ C according to the NeoART- trial: Blood sample collection, processing and storage SOP . NB. The Sponsor representative should be notified in instances where the storage freezer temperature deviation from -80 $^{\circ}$ C by more than +/-10 $^{\circ}$ C

These samples will be used for genomic and proteomic analysis. Blood samples will be suitably stored in the pathology department of each site till required for batch analysis. When requested for batch analysis at various recruitment time points throughout the study, blood samples will be transferred for centralised study sample storage under the Human Tissue Authority License/ Permit to Import or Export of Human Tissues or Part Thereof Health Office/District Health Office (BLESS)

The Sponsor 'Record of retained body fluids log' will be maintained throughout the study at each site to track all participant blood and Tumour samples accountability and location. These completed logs should be made available upon request at study monitoring visits.

Tumour samples will be derived from tumour biopsies performed during colonoscopy and surgical samples following surgery. Any excess tumour tisue left over after the tissue sample has been processed for routine diagnostic purposes will be utilised. Formalin fixed, paraffin embedded blocks will be prepared and stored in the pathology department of each site till requested for batch analysis. All tissue samples will be transferred for centralised study sample storage under the Human Tissue Authority License/ Permit to Import or Export of Human Tissues or Part There of Health Office/District Health Office (BLESS).

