#### 15.2 Data collection tool

Case Report Forms will be designed by the CI and the CI delegate and the final version will be approved by the Sponsor.

It is the Investigator's responsibility to ensure the accuracy of all data entered and recorded in the CRFs. The Staff Delegation of Responsibilities Log will identify all trial personnel responsible for data collection, entry, handling and managing the database. Basic demographic and clinical information will be gathered at the time of the initial interview and by review of the medical notes if needed. The following information will be recorded for all subjects in the CRF:

- Demographic details: Date of enrolment, age, gender, ethnicity
- Clinical data: symptomatology, risk factors for development of CRC, weight, height, vital signs
- Findings at endoscopy
- Imaging: findings of ultrasound, CT and/or MRI (performed as clinically indicated)
- Disease staging: TNM staging prior to surgery and definitive histological staging (TNM, Duke's stage)
- Histology: routine histological grading, apoptosis count and specialist assays (see below)
- Concomitant medication: a full record of all non-study drugs taken will be kept
- Study-drug treatment: compliance with study medication, all adverse events, serious or otherwise
- Validated Quality of Life Tool (EORTC QLQ C-30, EuroQol EQ-5D, QLQ-CR29)

The following blood sample analysis will be performed:

- Baseline FBC, urea and electrolytes, LFTs, CEA, pre-treatment serum sample for study molecular analyses
- Day 14/15 of treatment FBC, urea and electrolytes, LFTs, CEA, post-treatment serum sample for study molecular analyses
- Day 28 FBC
- Day 42 (4 weeks post-surgery) FBC, urea and electrolytes, LFT, CEA
- 6 monthly visits for 5 years following surgery CEA
- Serum plasma samples will be taken at baseline (Day 1) and end of treatment (Day 14), processed and stored at -80°C (+/- 10°C) for future analyses
- Any other blood or clinical sample at any time if deemed necessary by the investigators in case of a suspected adverse event

All laboratory analysis should be reviewed by the PI and where results reported are not within the normal range the PI must clearly annotate 'Not clinically Significant' or 'Clinically Significant' and sign and date the results. The relevant results should be carefully transcribed to the Case Report Forms.

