#### 17.2.2 Secondary endpoints

Secondary endpoints will include:

- Overall survival at 2 and 5 years
- Recurrence free survival at 5 years
- Colon cancer specific death at 2 and 5 years
- Artesunate drug related toxicity
- Adverse events
- Pathological assessment of tumour regression (involvement of lymph nodes; serosa; resection margin)
- Quality of life (EuroQol EQ-5D, EORTC QLQ C-30, EORTC QLQ-CR29)
- Surgical morbidity/mortality
- Predictive value of tumour biomarkers in terms of predicting response to artesunate therapy
- Biomarker and molecular profiling studies

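### The tumour regression endpoint records node, serosa and margin status once, at resection: its absolute response rates cannot be read as regression, and the planned test leaves recorded baseline stage unused

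*Protocol*

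**What the plan says.** Protocol section 17.2.2 lists the endpoint as "Pathological assessment of tumour regression (involvement of lymph nodes; serosa; resection margin". The synopsis and section 5.1 specify it in the same way. No responder rule and no regression grade is given.

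Section 17.3.3.3 gives the analysis: "Pathological tumour response will be assessed for all patients and comparisons examined using the chi-squared test with 95% confidence intervals expressed for response rates".

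Four other places bear on it:

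- Section 9.1 admits "Stage II/III colorectal cancer planned for surgical resection and no clinical indication for neoadjuvant preoperative chemotherapy/chemoradiation therapy". Nodal status at entry is therefore mixed, and the split between stages is not stated.
- Section 15.2 puts on the CRF "Disease staging: TNM staging prior to surgery and definitive histological staging (TNM, Duke's stage". A clinical T and N stage before surgery is thus recorded for each patient.
- The histology line of section 15.2 reads "Histology: routine histological grading, apoptosis count and specialist assays (see below". It names no regression score.
- Section 12.5.1.1 says "Tumour samples will be derived from tumour biopsies performed during colonoscopy and surgical samples following surgery". The only pre-treatment tissue is a biopsy of the primary.

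**The concern.** Regression is a change from an earlier state, whereas the three listed items are states observed once, after treatment. There is no earlier pathological status for nodes or serosa, and a resection margin does not exist before the resection. A patient with clear nodes at surgery may have been cleared by treatment or may never have had nodal disease, and these items cannot tell the two apart.

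The trial's rationale (section 6.11) includes shrinkage of the primary tumour before surgery. A published pathological response rate would be taken as evidence of that, although its level would largely reflect the stage mix at entry. Separately, stage at entry is a strong candidate predictor of involvement at resection. The plan collects it and then compares arms without it, which gives up precision at no saving.

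**Working it through.** **The plan's own figure.** There is none to reproduce. The only sample size calculation (section 17.3.1) concerns recurrence. No rate or power is stated for pathological response, so the figures below are illustrations under stated assumptions.

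**Inputs**

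- From the protocol: 1:1 allocation (11.2) and 200 patients (17.3.2), so about 100 per arm; significance at two-sided 5%, taking the 5% level in 17.2.1 and 17.3.3.1 as two-sided.
- Assumed: response means no nodal involvement at resection; placebo clears no involved nodes; artesunate clears a fraction r of node-positive patients; a share s of patients was never node-positive.

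**Step 1: the level of the rate.** Placebo rate p0 = s. Artesunate rate p1 = s + (1 − s)r. Difference d = (1 − s)r. The placebo rate equals s with no regression at all. The true clearance r is seen only after multiplication by (1 − s).

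**Step 2: dilution of the difference.** Let m = (p0 + p1)/2 and n = 100. Power of the chi-squared comparison is

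Φ{ [d − 1.96·√(2m(1 − m)/n)] / √([p0(1 − p0) + p1(1 − p1)]/n) }.

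| r | s | Placebo | Artesunate | Difference (points) | Power |
|---|---|---|---|---|---|
| 20% | 30% | 30% | 44% | 14 | 54% |
| 20% | 50% | 50% | 60% | 10 | 29% |
| 20% | 70% | 70% | 76% | 6 | 16% |
| 30% | 40% | 40% | 58% | 18 | 72% |
| 30% | 50% | 50% | 65% | 15 | 57% |
| 30% | 60% | 60% | 72% | 12 | 43% |

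The test does carry the drug effect, since its power exceeds 5% throughout. The level of the rate says nothing about regression.

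**Step 3: using the recorded clinical N stage.** Take s = 50%, r = 30%, and clinical N stage correct with probability a in both node-positive and node-negative patients. Half the patients are then clinically node-positive. The non-involvement rates are:

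- Placebo: 1 − a in clinical N-positive, a in clinical N-negative. Average within-stratum variance V0 = a(1 − a).
- Artesunate: q1 = 1 − 0.7a and q2 = 0.3 + 0.7a. V1 = ½[q1(1 − q1) + q2(1 − q2)].

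With SE = √((V0 + V1)/100) and d = 0.15, power is Φ(0.15/SE − 1.96).

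| Analysis | V0 | V1 | SE | Power, formula | Power, simulation |
|---|---|---|---|---|---|
| Unadjusted | 0.2500 | 0.2275 | 0.0691 | 58% | 58–60% |
| Adjusted, a = 65% | 0.2275 | 0.2165 | 0.0666 | 61% | 60–61% |
| Adjusted, a = 75% | 0.1875 | 0.1969 | 0.0620 | 68% | 64–67% |
| Adjusted, a = 85% | 0.1275 | 0.1675 | 0.0543 | 79% | 77–78% |

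The simulation ranges come from repeated runs of 1,500 to 6,000 trials per setting, using a linear probability model with clinical N stage as covariate. The closed formula is slightly optimistic.

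**Step 4: sensitivity to clearance** (simulation, s = 50%). At r = 20%, power goes from about 31% to 31–32%, 36% and 45% at the three accuracies. At r = 10%, it goes from about 12% to 11–12%, 12% and 16%. The gain is near zero at 65% accuracy throughout, and at most about 4 points at 10% clearance. Serosa and margins were not simulated.

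**The case against.** The strongest reply is that the protocol nowhere equates absence of involvement with response. The parenthesis may simply list what the pathologist looks at, and a responder rule for a secondary endpoint can properly be left to an analysis plan that is not shown. That stands: a reader might infer that the protocol counts never-involved placebo patients as responders, but this is an inference from the listed components and not a written rule. The components themselves are nevertheless fixed in three places, and section 15.2 names no histology from which a graded regression score would come.

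A reader might also infer that the endpoint cannot detect regression, or that the chi-squared test is invalid. The documents do not support this. Section 11.2 states: "Participants recruited to the study will be randomised to receive either artesunate or placebo 1:1". Never-involved patients are expected equally in both arms, so the difference in involvement is a valid, if diluted, estimate of the treatment effect. An unadjusted test is valid in a randomised trial.

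Nor is this the only efficacy information before two years. Section 17.3.3.1 plans recurrence-free proportions beyond one year, CEA is measured repeatedly (12.3), and biomarkers are a listed endpoint.

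Finally, a baseline is not wholly absent. Pre-surgery TNM is recorded, so a change from clinical stage could be derived, with staging error. The planned analysis does not use it.

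**Conclusion.** A minor point that holds. The label, the three components and the response-rate analysis do not match: single findings at resection, in a mixed Stage II/III population without pre-treatment pathology of those sites, give absolute rates that cannot be interpreted as regression. The between-arm difference can be interpreted, as an effect on disease extent at surgery.

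The efficiency loss from ignoring clinical stage depends entirely on assumptions outside the protocol. In the nodal example at 30% clearance, adjustment adds about 1 to 2 points of power at 65% staging accuracy and close to 20 points at 85%. At 10% clearance it adds at most about 4. The protocol claims no power for this endpoint, so no stated figure is wrong, and the primary result is unaffected.

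**What to change.** In sections 5.1, 17.2.2 and 17.3.3.3, and in the matching synopsis line:

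1. Rename the endpoint as the proportions of patients who are node-positive, serosa-involved and margin-positive at resection. Report the three separately by arm.
2. Compare arms with a binomial or logistic model adjusted for pre-treatment clinical N stage (nodes) and T stage (serosa), giving a standardised risk difference with a 95% confidence interval. For margins, keep an unadjusted or exact comparison if events are few.
3. State that the absolute rates are not response rates and that only the between-arm difference will be interpreted.

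The cost is a change of wording and the use of covariates that section 15.2 already collects ("Disease staging: TNM staging prior to surgery and definitive histological staging"). No new visits, samples or patients are needed. The downside is a less attractive label and slightly more analysis work.
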